3.1.1 Questions Regarding Key Monitoring Behavior

Question 1:

What is your medical specialty*? Please select one from the drop-down list below.

- O General Medicine/General Practice
- O Neurology
- O Psychiatry
- O Other SPECIFY:

* NOTE – OTHER SPECIALTIES TO BE INCLUDED BASED ON AUDIENCES TO WHOM MATERIAL WAS SENT

Question 2

Please think about your patients with schizophrenia, bipolar disorder, and/or major depressive disorder who are treated with Seroquel® or Seroquel® XR. Describe the "monitoring" of metabolic factors^{*} potentially related to treatment with Seroquel® or Seroquel® XR.

A. What proportions of your patients are being monitored by you, someone else in your practice or are referred to other healthcare providers? _____%

B. What proportion of your patients is referred to other healthcare providers for monitoring?

*Monitoring of metabolic factors includes: weight at initiation and during continuing treatment, ordering or reviewing lipid panel tests, observing patients for signs or symptoms associated with hyperglycaemia, ordering or reviewing tests for blood glucose measurement for patients with diabetes mellitus or in patients with risk factors for diabetes mellitus for worsening of glycaemic control, and counseling on nutrition, exercise and maintaining a healthy lifestyle

Question 3

Thinking now of the patients that you (or someone in your practice) monitor for metabolic issues potentially related to treatment with Seroquel® or Seroquel® XR, which of the following activities do you do? Please check all that apply.

- [□] I counsel patients taking Seroquel® or Seroquel® XR on healthy eating, exercise, and healthy lifestyle improvements
- ^D I monitor patients' weight at the initiation of treatment with Seroquel® or Seroquel® XR
- ^a I monitor patients' weight on a regular basis after initiating treatment with Seroquel® or Seroquel® XR
- I monitor tests for hyperlipidemia in patients who are taking Seroquel or Seroquel® XR
- [□] I observe for signs and symptoms of hyperglycaemia in patients who are taking Seroquel® or Seroquel® XR
- I monitor patients with diabetes mellitus or with risk factors for diabetes mellitus for worsening of glucose control if they are taking Seroquel® or Seroquel® XR

Question 4

The following question has two parts; please respond to both parts of the question.

- A. Did you receive educational information relevant to the issues in this survey from AstraZeneca, either as a mailing or from a company representative, in (INSERT LOCAL MARKET REFERENCE MONTH) 2012 regarding the Product Label for Seroquel® or Seroquel® XR?
- O Yes
- O No
- O Unaware/not sure
- B. Did you read the educational information?

Risk Minimization Physician Survey Protocol Drug Substance Quetiapine fumarate Study Code: D1443C000127 Edition Number: 1 Date: 19 December 2012

- O Yes
- O No
- O Unaware/not sure

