1. BACKGROUND

The MEB, as the Reference Member State (RMS) for SEROQUEL and SEROQUEL XR, requested AstraZeneca to update the education materials in scope of the EU Risk Management Plan (RMP) and Summary of Product Characteristics (SmPC) changes with respect to hyperglycaemia and metabolic monitoring. The content and the messages for these educational materials have been agreed and distribution in the individual member states is ongoing.

AstraZeneca was also requested to provide a plan for assessing the effectiveness of these educational materials. During discussion with the MEB, it was communicated that there are 2 components to the assessment of effectiveness: process indicators (receipt and understanding of materials) and outcome indicators (changes in behaviour and effect on patients). To realize these 2 indicators, AstraZeneca is proposing 2 components for the evaluation of the effectiveness of the metabolic education: an objective, easy to understand and complete healthcare provider survey and the use of an Electronic Medical Records approach, as a potential means to assess the monitoring of patients.

This protocol describes the evaluation of the effectiveness of the distribution of metabolic educational materials sent to healthcare providers in the EU. It will be conducted via an evaluation survey that uses a questionnaire to assess the receipt of the educational material, whether the material was read, and to assess healthcare provider behaviour regarding the conduct of monitoring of metabolic parameters for patients treated with SEROQUEL and SEROQUEL XR. The survey will be conducted among healthcare providers who were targeted to receive the educational materials following local guidance and directives.

A companion proposal describes the evaluation of electronic medical record (EMR) data including details on objectives, the source of data, and the target healthcare provider-base for the database assessment.

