3.1 Study Design

This survey will be completed by a sample of healthcare providers who were targeted to receive the metabolic educational materials and either currently prescribe or have the potential to prescribe SEROQUEL or SEROQUEL XR. A sample of healthcare providers who were targeted for the educational materials will be approached to participate in the survey.

The survey will be administered using the following modality:

• Self-administered and Internet-based questionnaire accessed through a secure website instructing the participant to enter a unique code provided in the invitation.

The survey will begin with screening questions to confirm respondent eligibility to participate in the survey. Completion of the entire survey is expected to take less than 10 minutes.

The survey included in Appendix B is written to reflect the wording and screen-by-screen presentation of questions for an Internet-based survey administration.

All respondents who complete the survey and who provide their contact information will be mailed a fee consistent with approved market value for the physician's time for completing the survey.

The questions related to having received the educational materials and having read the information (measures of process) are closed-ended questions (answered affirmatively as yes/no/unsure response options). Questions related to physician behavior regarding monitoring of patients (measures of outcome) are percentage estimates provided by the physician.

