4.2 Survey Administration

Healthcare providers who select to participate in the survey will be directed to a secure website where they will be instructed to enter a unique code to access the survey. The questionnaire will begin with a screening module that includes questions to verify that the respondent has met all of the inclusion criteria and none of the exclusion criteria for the survey. Respondents will provide their consent to participate in a study that is designed for market research purposes and not intended to be promotional in any way. Respondents are asked not to share the content of the survey.

Depending on the answers to the screening questions, survey participation could either be terminated or continued. If deemed ineligible, respondents will be immediately notified with a "thank you" message that the survey participation has ended and they will not receive compensation. If deemed eligible, respondents will be allowed to continue survey participation.

The data entry system used for the survey will be secure for receiving and storing survey data. Prescriber-identifying information will be stored separately from survey data.

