6. ANALYSIS

The survey questionnaire contains questions about the specialty of the physician sample completing the survey, questions specific to whether referrals are made to other healthcare providers for metabolic monitoring, whether the healthcare provider conducts monitoring of patients, general questions regarding receipt of the educational materials, and behavior about reading the materials. Information obtained from responses to each question of the survey will be reported as descriptive statistics. A frequency distribution of responses to each question (the number of respondents who give answers to each response option) will be presented.

Each risk minimization behavior will be evaluated individually.

Related behaviors, such as:

- Monitoring for weight
- Monitoring for signs and symptoms of hyperglycaemia and monitoring blood glucose changes in patients with diabetes mellitus will be combined to report the number of survey respondents who answered each risk minimization activity individually, any one activity and both activities. This will be expressed as a percent of the total number of respondents who answered the questions on these risk minimization activities.

Frequency distributions of the responses to having received SEROQUEL[®] / SEROQUEL[®] XR educational materials and behaviors about reading the educational materials, will also be calculated and displayed. The analysis of frequencies will include exact binomial 95% confidence intervals.

The following will be reported, as appropriate, as part of this analysis:

- The number of invitations issued to healthcare providers
- The number of healthcare providers screened for participation
- The number of healthcare providers eligible for participation
- The number of healthcare providers who completed the survey

- Description of healthcare provider survey participants, including:
 - Specialty of respondent
 - Country of practice
- Frequency distribution of responses to each survey question (the number of respondents who give each answer to each question)
- Percent of respondents selecting desired response to each question relating to each risk minimization activity and 95% confidence interval
- Percent of respondents demonstrating success of composite risk minimization activities and 95% confidence interval

Additional analyses may be performed as needed.

Risk Minimization Physician Survey Protocol

Drug Substance	Quetiapine fumarate
Study Code	D1443C000127
Edition Number	1

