Appendix B Questionnaire

QUESTIONNAIRE

The questionnaire is designed to be administered as an on-line survey via Internet. The following are mock-up version of what the successive screens that would be displayed

Screen 3 Question 1:

What is your medical specialty*? Please select one from the drop-down list below.

- O General Medicine/General Practice
- O Neurology
- O Psychiatry
- O Other SPECIFY:

* NOTE – OTHER SPECIALTIES TO BE INCLUDED BASED ON AUDIENCES TO WHOM MATERIAL WAS SENT

Screen 4 Question 2:

Instructions: Please think about your patients with schizophrenia, bipolar disorder, and/or major depressive disorder who are treated with Seroquel® or Seroquel® XR. Describe the "monitoring" of metabolic factors^{*} potentially related to treatment with Seroquel® or Seroquel® XR.

- What proportions of your patients are being monitored by you, someone else in A. your practice or are referred to other healthcare providers? %
- What proportion of your patients is referred to other healthcare providers for B. monitoring? %

*Monitoring of metabolic factors includes: weight at initiation and during continuing treatment, ordering or reviewing lipid panel tests, observing patients for signs or symptoms associated with hyperglycaemia, ordering or reviewing tests for blood glucose measurement for patients with diabetes mellitus or in patients with risk factors for diabetes mellitus for worsening of glycaemic control, and counseling on nutrition, exercise and maintaining a healthy lifestyle

Screen 5 Question 3:

Instructions: Thinking now of the patients that you yourself monitor for metabolic issues potentially related to treatment with Seroquel® or Seroquel® XR, which of the following activities do you perform? Please check all that apply.

GEL Version ID: CNS.000-362-594.2.0 Approved Date Printed: 04-Jan-2013 Approved by [name] 21 Dec 2012 15:02:47

- ^a I counsel patients taking Seroquel® or Seroquel® XR on healthy eating, exercise, and healthy lifestyle improvements
- I monitor patients' weight at the initiation of treatment with Seroquel® or Seroquel® XR
 I monitor patients' weight on a regular basis after initiating treatment with Seroquel® or
- Seroquel® XR
- [□] I monitor tests for hyperlipidemia in patients who are taking Seroquel or Seroquel® XR
- I observe for signs and symptoms of hyperglycaemia in patients who are taking Seroquel® or Seroquel® XR

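### Question 2 asks for a percentage of treated patients but not how many there are, so no patients cannot be told from a true 0%, and results describe providers only (minor, optional improvement)

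*Protocol*

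**What the plan says.** Section 3.1 describes the outcome items as follows: "Questions related to physician behavior regarding monitoring of patients (measures of outcome) are percentage estimates provided by the physician". Question 2 is the only item answered with a percentage, so it is the item this description fits. Part A asks "What proportions of your patients are being monitored by you, someone else in your practice or are referred to other healthcare providers"; part B, in Appendix B, begins "What proportion of your patients is referred to other healthcare providers for" and ends with monitoring. Both refer to the provider's own patients on the product, and neither asks for a count.

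Section 3.2.1 admits current prescribers and also providers who might prescribe. The screening module is described in Section 4.2 as containing "questions to verify that the respondent has met all of the inclusion criteria and none of the exclusion criteria for the survey". Section 6 lists the questionnaire content as specialty, referral, monitoring, receipt and reading; caseload is not on the list. It reports each question as a frequency distribution, that is, "the number of respondents who give answers to each response option", and states no weighting.

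On purpose, Section 1 says the survey assesses healthcare provider "behaviour regarding the conduct of monitoring of metabolic parameters for patients treated with SEROQUEL and SEROQUEL XR", and Section 2 likewise speaks of provider behaviour. Section 1 names a separate electronic medical record component as a potential means of assessing the monitoring of patients.

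**The concern.** A percentage has meaning only if its denominator is above zero, and it can be moved to the patient scale only if that denominator is known. Question 2 provides neither safeguard.

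First, an eligible provider may have no patient on the product. The form offers a percentage blank and nothing else. Such a provider may enter 0%, enter some habitual figure, or leave it empty, and the data will not show which happened. A 0% of this kind would be read as absence of monitoring.

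Second, Question 2 is phrased in terms of patients, so its results are easily read as the share of treated patients who are monitored. Without caseloads that share cannot be calculated. An analysis plan cannot repair this afterwards, because the questionnaire fixes what is collected. Specialty (Question 1) is at best a rough stand-in for caseload.

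**Working it through.** **Is a caseload collected anywhere?** Question 2 asks for two percentages in both Section 3.1.1 and Appendix B. Questions 1, 3 and 4 cover specialty, activities, and receipt and reading. Appendix B as available starts at Screen 3, so the absence of a caseload item on earlier screens is inferred from Sections 4.2 and 6, not read directly.

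**What the plan's own precision figures describe.** Table 1 in Section 3.3 follows p ± 1.96 × √(p(1 − p)/100), cut off at 0. At p = 0.51 the half-width is 1.96 × √(0.51 × 0.49/100) = 0.098, giving 41.2% to 60.8% as printed. At p = 0.81 it is 0.077, giving 73.3% to 88.7% as printed. All 17 rows reproduce. The table is therefore for a yes/no rate among 100 equally counted respondents, and its largest half-width is 9.8 points. It does not describe a patient-weighted share.

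**Effect of respondents with no treated patients.** Suppose k of the 100 respondents in a country have none and enter 0%. The zero category then rises by k percentage points. If a mean were also reported and the others averaged 60% (assumed), it would be (100 − k)/100 × 60 = 60 − 0.6k. The documents give no value for k, and k may be 0.

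**Provider average against patient share.** Let provider i treat nᵢ patients and report pᵢ.

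- Provider average: U = Σpᵢ/N
- Patient share: W = Σnᵢpᵢ/Σnᵢ
- Difference: W − U = cov(n, p)/mean(n), which is zero when caseload and monitoring are uncorrelated

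All caseloads below are assumptions, with half of the providers in each group.

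| Smaller caseload | Larger caseload | U | W |
|---|---|---|---|
| 3 patients, 40% | 30 patients, 80% | 60% | (1.2 + 24)/33 = 76.4% |
| 5 patients, 50% | 25 patients, 70% | 60% | (2.5 + 17.5)/30 = 66.7% |
| 3 patients, 70% | 30 patients, 50% | 60% | (2.1 + 15)/33 = 51.8% |
| 2 patients, 100% | 50 patients, 20% | 60% | (2 + 10)/52 = 23.1% |
| 2 patients, 20% | 50 patients, 100% | 60% | (0.4 + 50)/52 = 96.9% |
| any, 70% | any, 70% | 70% | 70% |

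The fourth and fifth rows give the same set of reported percentages, so the planned data could not tell them apart. The direction of any gap is not known in advance.

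**The case against.** The strongest reply is that the protocol never undertakes to estimate a share of patients. Sections 1, 2 and 3.1 all speak of provider behaviour, Section 6 reports numbers and percents of respondents, and Table 1 is built on completed questionnaires. Where materials are sent to providers, the provider is a proper unit and counting each one once is the natural analysis. Section 6 names no mean of Question 2 as an estimate for patients, and a distribution of providers is not biased by caseload. Patient monitoring is given to the medical record component. All of this stands.

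A reader might infer from the table that the survey's outcome result is biased, or that a gap of 16 points overrides the stated precision of 6 to 10 points. The documents support neither. The gap rests wholly on assumed caseloads, and it is a difference between two target quantities, whereas the stated precision is sampling error for one of them. Nor do the documents show that a planned comparison with the medical record results would fail: this protocol plans none, and the companion proposal is not available.

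Two further replies have partial force. Question 2 can be tabulated by specialty, but caseload differences within a specialty remain. Section 3.4 draws the sample from providers considered likely to prescribe, which should reduce the number with no treated patients but does not rule them out.

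What the reply leaves untouched is the ambiguous zero, which affects the provider-level distribution itself.

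**Conclusion.** The concern holds as a minor, optional improvement, not as an error in the provider-level analysis. Question 2 has no denominator, so an answer from a provider with no treated patients cannot be separated from a true 0%, and the results describe providers, not the proportion of treated patients monitored. Equal counting of respondents is legitimate for the stated aim.

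The size cannot be determined from the documents. It depends on how many respondents have no treated patients and how they answer, and on whether monitoring varies with caseload. Both effects may be zero. The conclusion also assumes that the screens not shown hold no caseload item, as Sections 4.2 and 6 suggest.

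**What to change.** On Screen 4, before 2A, and correspondingly in Section 3.1.1, add one numeric field for the approximate number of patients the provider currently treats with Seroquel or Seroquel XR, with zero allowed.

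In Section 6:

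- Report Question 2 among providers with at least one treated patient as the main provider-level distribution, and give the number with none.
- State that this distribution is not a share of patients.
- Add, per country, the caseload-weighted percentage Σnᵢpᵢ/Σnᵢ as a secondary descriptive figure, with an interval obtained by resampling providers.

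The cost is one short item in a survey expected to take under 10 minutes, and one more table. The caseload is itself a provider's estimate, and the weighted figure will be less precise and can be dominated by a few providers with many patients; that is why it should stay secondary.

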3.2 Study Population

3.2.1 Inclusion Criteria

Health Care Professionals who were targeted to receive the metabolic educational materials and either currently prescribe or have the potential to prescribe SEROQUEL or SEROQUEL XR.

Each physician should meet all inclusion criteria and none of the exclusion criteria to be eligible for this survey. Under no circumstances can there be any exceptions to this rule.

3.2.2 Exclusion Criteria

Healthcare providers or their immediate family members who have been employed by AstraZeneca or for a European Regulatory Agency are not eligible to participate.

3.3 Sample Size

A sample size of 100 completed questionnaires from healthcare providers in each of eight selected countries representing the geographic diversity of the EU is proposed. The size of the sample was determined based on both practical and statistical considerations. There is no presumed target rate for success in risk minimization measures based upon either a process measure (e.g., receiving educational materials) nor is there a rate specified *a priori* for success in outcome measures (e.g., metabolic monitoring). A sample of 100 completed questionnaires will allow estimation of the rate for process and outcome measures with a moderate degree of precision (within 6-10 percentage points regardless of the actual level of the process or outcome measure). The table below shows the precision of the estimates for level process and outcome measure using two-sided 95% confidence intervals (CIs) obtained with the sample size of 100 completed surveys. The noted CIs are used to indicate that for any survey-estimated level of effectiveness of risk minimization, the true population level of effectiveness is at least as high as the lower limit of the 95% CI and may be as high as the upper limit of the 95% CI.

Table 1:Precision of estimated Rates of effectiveness of risk minimization
including: 1) Receiving information (as Process measure) or 2)
performance of metabolic monitoring (as Outcome measure) with a
Sample Size of 100 (Two-sided 95% Confidence Interval)

Estimated Rate	95% Confidence Interval Lower Limit	95% Confidence Interval Upper Limit
1%	0.0%	3%
6%	1.3%	10.7%
11%	4.9%	17.1%
16%	8.8%	23.2%
21%	13%	29%
26%	17.4%	34.6%

Estimated Rate	95% Confidence Interval Lower Limit	95% Confidence Interval Upper Limit
31%	21.9%	40.1%
36%	26.6%	45.4%
41%	31.4%	50.6%
46%	36.2%	55.8%
51%	41.2%	60.8%
56%	46.3%	65.7%
61%	51.4%	70.6%
66%	56.7%	75.3%
71%	62.1%	79.9%
76%	67.6%	84.4%
81%	73.3 %	88.7%

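### Table 1 (Section 3.3) shows normal-approximation limits although Section 6 plans exact binomial intervals, and its 6-to-10-point summary does not hold at every rate

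*Protocol*

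**What the plan says.** Protocol Section 3.3 proposes "A sample size of 100 completed questionnaires from healthcare providers in each of eight selected countries". It sets no success criterion: "There is no presumed target rate for success in risk minimization measures". The statistical part of the rationale is therefore precision, which is summarised as "within 6-10 percentage points regardless of the actual level of the process or outcome measure". Table 1 is offered as the evidence, "using two-sided 95% confidence intervals (CIs) obtained with the sample size of 100 completed surveys". The section does not name the interval method and does not describe the table as an approximation.

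Protocol Section 6 does name a method: "The analysis of frequencies will include exact binomial 95% confidence intervals". This sentence comes directly after the one on whether the materials were received and read. The later list items on the risk minimization activities and their composites ask for a 95% interval without naming a method.

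**The concern.** A precision table should show the intervals that the analysis will report. If Table 1 was computed by one method and Section 6 prescribes another, a reader who plans from the table will expect limits that the report will not contain. Receipt of the materials is the process measure named in the title of Table 1, and it is also a measure to which the exact-interval sentence clearly applies. The two sections therefore meet on the same quantity.

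The choice of method matters most at very low or very high rates, where the Wald interval is symmetric and the exact interval is not. Section 3.3 reads the lower limit as a floor for the true level of effectiveness, so a lower limit set too high at high rates is the unfavourable direction. At low rates, where distribution of the materials would have failed, an upper limit set too low makes the result look more certain than it is.

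The summary sentence is a second matter. It claims a range of 6 to 10 points at any rate, and the first two rows of Table 1 already fall outside that range.

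**Working it through.** **Inputs.** n = 100 completed questionnaires in one country, two-sided 95% level, and the 17 rates of Table 1 (all from Section 3.3). Exact binomial intervals (Section 6).

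**Step 1: reproduce Table 1.** The Wald limits are p ± 1.96 × √(p(1−p)/100), cut at 0.
- 1%: 1.96 × √(0.01 × 0.99/100) = 1.95 points, giving 0.0% (cut) to 2.95%. Printed: 0.0% to 3%.
- 6%: 1.96 × √(0.06 × 0.94/100) = 4.65 points, giving 1.3% to 10.7%. Printed: the same.
- 51%: 1.96 × √(0.51 × 0.49/100) = 9.80 points, giving 41.2% to 60.8%. Printed: the same.
- 81%: 1.96 × √(0.81 × 0.19/100) = 7.69 points, giving 73.3% to 88.7%. Printed: the same.

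All 17 rows match to the printed rounding. Neither the exact (Clopper-Pearson) nor the Wilson interval reproduces the table; at 6% they give 2.2–12.6% and 2.8–12.5%.

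**Step 2: exact limits.** For x of 100, the lower limit is the 2.5% quantile of Beta(x, 101−x) and the upper limit is the 97.5% quantile of Beta(x+1, 100−x). One limit can be checked by hand: at x = 1 the lower limit is 1 − 0.975^(1/100) = 0.03%.

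| Rate | Table 1 (Wald) | Wald half-width | Exact | Estimate to farther exact limit |
|---|---|---|---|---|
| 1% | 0.0–3 | 2.0 | 0.03–5.4 | 4.45 |
| 6% | 1.3–10.7 | 4.7 | 2.2–12.6 | 6.60 |
| 11% | 4.9–17.1 | 6.1 | 5.6–18.8 | 7.83 |
| 16% | 8.8–23.2 | 7.2 | 9.4–24.7 | 8.68 |
| 21% | 13–29 | 8.0 | 13.5–30.3 | 9.29 |
| 26% | 17.4–34.6 | 8.6 | 17.7–35.7 | 9.73 |
| 31% | 21.9–40.1 | 9.1 | 22.1–41.0 | 10.03 |
| 36% | 26.6–45.4 | 9.4 | 26.6–46.2 | 10.21 |
| 41% | 31.4–50.6 | 9.6 | 31.3–51.3 | 10.29 |
| 46% | 36.2–55.8 | 9.8 | 36.0–56.3 | 10.26 |
| 51% | 41.2–60.8 | 9.8 | 40.8–61.1 | 10.20 |
| 56% | 46.3–65.7 | 9.7 | 45.7–65.9 | 10.28 |
| 61% | 51.4–70.6 | 9.6 | 50.7–70.6 | 10.27 |
| 66% | 56.7–75.3 | 9.3 | 55.9–75.2 | 10.15 |
| 71% | 62.1–79.9 | 8.9 | 61.1–79.6 | 9.93 |
| 76% | 67.6–84.4 | 8.4 | 66.4–84.0 | 9.57 |
| 81% | 73.3–88.7 | 7.7 | 71.9–88.2 | 9.07 |

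**Step 3: the 10-point end.** Over all counts from 0 to 100, the farther exact limit is more than 10 points away for counts 31 to 69. The largest distance is 10.29 points, so the excess is at most 0.29. The largest exact half-width is 10.17 points, at 50%.

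**Step 4: the 6-point end.** The Wald half-width is below 6 for counts up to 10 and from 90 upwards. The farther exact limit is less than 6 points away for counts up to 4 and from 96 upwards. The lower end of the stated range therefore fails under either method, and in the favourable direction.

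**Step 5: where the methods part.** From 1% to 36% the Wald lower limit is below the exact one, so it is cautious. From 41% on it is above: by 0.1 point at 41% (31.4 − 31.3) and by 1.4 points at 81% (73.3 − 71.9). The largest upper-limit gaps are at the low end: 5.4 − 3 = 2.4 points at 1%, and 12.6 − 10.7 = 1.9 points at 6%.

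**The case against.** The strongest reply is that Table 1 is a planning display and every figure in it is computed correctly for the method used. Section 3.3 speaks of a moderate degree of precision in whole points, and rounded to whole points no exact limit lies more than 10 points from the estimate. The failure at the 6-point end means precision is better than claimed, and the table prints those rows openly. With no target rate, no decision turns on a shift of one or two points. All of this stands, and it limits the weight of the point. It does not remove the mismatch, because Section 3.3 neither names its method nor calls it an approximation.

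A second reply is that the exact-interval sentence may cover only receipt and reading. That is a fair reading of Section 6. Even so, receipt is the process measure in the title of Table 1, so the mismatch remains for at least that measure.

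A reader might go further and infer that the survey fails to deliver its stated precision, or that 100 per country is too few. The figures do not support this: the ceiling moves by at most 0.29 points. Nor is precision the only ground for the sample size, since Section 3.3 also cites practical considerations.

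A reader might also infer, because Section 6 lists "Country of practice" only among respondent characteristics, that country-level estimates are not planned. The protocol does not say so. Section 3.3 ties the 100 to each country, and the layout by country, pooling and weighting may properly be left to a statistical analysis plan that is not at hand.

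**Conclusion.** The point holds in a limited form. Table 1 gives Wald limits, while Section 6 plans exact limits for at least receipt and reading, so the table does not describe the planned intervals. The effect is slight in mid-range (10.3 points against 10) and larger at the ends: the upper limit rises by 2.4 points at a rate of 1% and by 1.9 at 6%, and the lower limit falls by 1.4 at 81%. Independently of the method, the claim of 6 to 10 points at every rate is wrong as written, because intervals are narrower near 0% and 100%.

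The sample size remains adequate for precision of about 10 points per country, and no conclusion of the survey depends on the difference. This is a correction of a stated figure and not a design fault.

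The figures assume 100 answers in the denominator for one country and binomial sampling. An item with fewer answers would have wider intervals under both methods.

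**What to change.** In Section 3.3, replace the limits in Table 1 with the exact (Clopper-Pearson) limits shown above and name the method. Replace the precision sentence with: *with 100 completed questionnaires per country, the exact 95% limits lie at most about 10 (10.3) percentage points from the estimate, and closer near 0% and 100%.*

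If the sponsor prefers to keep Table 1, the least that is needed is to label it as a Wald planning approximation that differs from the intervals of Section 6. The summary sentence still has to change.

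The cost is one recalculated table and one sentence. The sample size does not change. The only downside is that the stated precision becomes slightly less favourable.
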